#### **9.2.6 Follow-up**

Each member of the study cohort will be followed from the start date until the first of the following termination dates:

- End of enrolment in the database
- Death
- End of study period (for DUS2, 31 December 2014)

For each member of the study cohort, comorbidity will be assessed for the entire period of data availability before the start date.

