**Table 7. Proposed Changes in the Labelling of Cilostazol and Characterisation of Users**

Proposed Change to Summary of Product Characteristics	Characterisation in DUS
Restricted target population	
Indication	
4.1 Cilostazol is for second-line use in patients in whom life-style modifications (including smoking cessation and [supervised] exercise programmes) and other appropriate interventions have failed to sufficiently improve their intermittent claudication symptoms	Smoking status a
4.2 The physician should reassess the patient after 3 months of treatment with a view to discontinuing cilostazol where an inadequate effect is observed.	Number of patients seen by the treating physician after 3 months b Number of patients discontinuing after 3 months b
Contraindications	
4.3 Patients with unstable angina pectoris, myocardial infarction within the last 6 months, or a coronary intervention in the last 6 months	Unstable angina Myocardial infarction Coronary intervention
Patients treated concomitantly with two or more additional antiplatelet agents (e.g., aspirin, clopidogrel)	Concurrent use of two or more platelet-aggregation inhibitors
Other SmPC changes	
Warnings and precautions	
4.4 Based on its mechanism of action, cilostazol may induce tachycardia, palpitation, tachyarrhythmia, and/or hypotension. The increase in heart rate associated with cilostazol is approximately 5 to 7 beats per minute; in patients at risk, this may induce angina pectoris.	
Patients who may be at increased risk for serious cardiac adverse events as a result of increased heart rate, e.g., patients with stable coronary disease or a history of tachyarrhythmias, should be monitored closely during the treatment with cilostazol; the use of cilostazol in patients with unstable coronary disease or coronary intervention within the last 6 months is contraindicated (see SmPC Section 4.3).	Number of visits to general practitioner and/or specialist

Proposed Change to Summary of Product Characteristics	Characterisation in DUS
Posology	
4.2 Reduction of the dose to 50 mg twice daily is recommended in patients receiving medicines that strongly inhibit CYP3A4, e.g., several macrolides, azole antifungals, protease inhibitors, or medicines that strongly inhibit CYP2C19, e.g., omeprazole.	Daily dose

CYP = cytochrome P-450; DUS = drug utilisation study; SmPC = Summary of Product Characteristics.

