  - Patients with a history of arrhythmias, hypotension, or coronary heart disease recorded at any time before the start date will be followed to assess the rates of visits to general practitioners or specialists. Visit rates for these patients will be used as a proxy of intensified monitoring and compared with the rates for the patients who do not have a history of arrhythmias, hypotension, or coronary heart disease.
- Posology
  - Daily dose of cilostazol at the start date will be assessed among concurrent users of potentially interacting medications at the start date
  - Reduction of daily dose to 50 mg will be assessed among patients who are prescribed a potentially interacting medication during continuous use of cilostazol.

The diagnosis, procedure, and medication codes that will be used to define the variables for the evaluation of the risk minimisation measures are included in Table 4 and Table 5.

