## **Sweden**

In Sweden, the national health care system provides universal coverage to all residents (9.4 million inhabitants). Health care coverage includes visits to general practitioners (GPs), specialists, hospital admissions, and hospital outpatient visits; drug costs are either partially or completely covered. A centralised civil registration system has been in place for many years, allowing for personal identification of each person in the entire population and for the possibility of linkage to all national registers containing civil registration numbers, e.g., patient register, cancer register, prescription databases, register of causes of death, and population registers (Furu et al., 2010). The National Inpatient Register covers all publicly run in-patient care in Sweden from 1987 and includes information on diagnoses, surgical procedures, and in-hospital deaths. Since 2001, the government has empowered the National Board to collect information on outpatient hospital care as well. The register includes about 1.5 million discharges annually. Since 1997, diagnoses have been coded using ICD-10 codes. Whereas coverage of the

---

 Population data from Eurostat. 2011. Available at: <http://epp.eurostat.ec.europa.eu/portal/page/portal/population/data/database>. Accessed 22 August 2012.

inpatient register is currently almost 100%, coverage of hospital-based outpatient care is considerably lower (about 80%) (Ludvigsson et al., 2011). Visits to GPs and specialists outside the hospitals are not included in the registers. Data collected in these registers can be made available for research purposes under the principles for protection and release of sensitive data (Ludvigsson et al., 2011; Ministry of Justice, 2009; 2012).

The Swedish National Prescription Database provides patient-level data on all dispensed and prescribed drugs (reimbursed and nonreimbursed) in ambulatory care to the whole population of Sweden since July 2005. The following data on drugs are available: drug substance, brand name, formulation and package, dispensed amount, dosage, expenditure and reimbursement, date of prescribing and dispensing, place of residence of the patient, practice issuing the prescription, and prescriber's specialty (Wettermark et al., 2007).

Data requests for research purposes require collaboration with university or affiliated researchers and ethics committee approval.

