### **9.7.5 Assessment of Changes to the Summary of Product Characteristics**

Analysis Tables 17, 18, and 26: The number and percentage of users by sex and age group (< 70 years, ≥ 70 years) will be calculated for the following conditions:

- Smoking: current, past, non-smoker (Analysis Table 17A)
- Number and percentage of users with at least one visit for any reason with a general practitioner or specialist between (a) 2 months and 4 months after the start date and (b) 1 month and 6 months after the start date, evaluated by the clinical review of a sample of patient profiles (Analysis Table 17B) and by diagnosis codes in all users (Analysis Table 17C). Analysis is restricted to patients who are current users of cilostazol at 3 months after the start date.
- Number and percentage of users with at least one visit for intermittent claudication with a general practitioner or specialist between (a) 2 months and 4 months after the start date and (b) 1 month and 6 months after the start date, evaluated by the clinical review of a sample of patient profiles (Analysis Table 17B) and by diagnosis codes in all users (Analysis Table 17C). Analysis is restricted to patients who are current users of cilostazol at 3 months after the start date.
- Discontinuation of cilostazol between 3 months and 4 months after the start date, evaluated using Kaplan-Meier survival curves (Analysis Table 17A and 26)

- Diagnosis within 6 months before the start date: unstable angina, myocardial infarction, or coronary intervention (Analysis Table 17A)
- Concurrent use of cilostazol and two or more platelet aggregation inhibitors (Analysis Table 17A)
- Reduction of daily dose of cilostazol from 200 mg to 100 mg among concurrent users of cilostazol and (a) potentially interacting medications (Analysis Table 18A) or (b) potent inhibitors of CYP3A4 or CYP2C19 (Analysis Table 18B) during continuous use of cilostazol

Analysis Table 19: Rates of visits to general practitioners and/or specialists among users at increased risk of serious cardiac events (patients with history of arrhythmias, coronary heart disease, or hypotension). Rates of visits per 100 person-years and 95% confidence intervals (CI) will be calculated for these patients and for those who are not considered at increased risk of serious cardiac events. Rate ratios and 95% CIs will be estimated comparing the rates in patients with increased risk with rates in patients without increased risk.

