### **9.7.9 Assessment of hospitalisations during treatment with cilostazol**

Analysis Table 22: Percentage of users of cilostazol with at least one hospitalisation for any cause during consecutive use of cilostazol.

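### Analysis Table 19 sets no on-treatment limit for visits or person-time, so its rate ratio can move between DUS1 and DUS2 without any change in monitoring during cilostazol treatment

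*Protocol*

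**What the plan says.** The label change in Table 7 is that patients at increased cardiac risk "should be monitored closely during the treatment with cilostazol". The only characterisation listed for that row is the number of visits to a general practitioner or specialist.

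Section 9.3.6 (warnings and precautions) defines the group by any earlier record of arrhythmia, hypotension or coronary heart disease, and the measure by how often these patients see a general practitioner or specialist once cilostazol has been started. It then says: "Visit rates for these patients will be used as a proxy of intensified monitoring", to be compared with the rates in patients without such a history.

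Section 9.7.5 gives the analysis (Analysis Table 19): "Rates of visits per 100 person-years and 95% confidence intervals (CI) will be calculated for these patients" and for the patients not at increased risk, followed by "Rate ratios and 95% CIs will be estimated comparing the rates in patients with increased risk with rates in patients without increased risk". Neither section says whether visits and person-years are counted only while the patient uses cilostazol.

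Section 9.2.6 defines follow-up in general: "Each member of the study cohort will be followed from the start date until the first of the following termination dates", which are end of enrolment, death and end of the study period. Stopping cilostazol is not among them.

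**The concern.** The measure being evaluated is monitoring during treatment. If follow-up has its Section 9.2.6 meaning, Table 19 also counts visits made after cilostazol was stopped, and these say nothing about how a treated patient is monitored. Because DUS1 runs for years and DUS2 for one calendar year, the mix of on- and off-treatment time would differ between the phases that Section 9.3.6 sets out to compare.

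A second issue is the comparison itself. The groups are defined by arrhythmia, hypotension or coronary heart disease, conditions that bring patients to a doctor whether or not anyone monitors more closely because of cilostazol. A ratio above 1 within one phase is therefore no evidence of intensified monitoring.

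Table 19 is the only analysis assigned to this label change, so no other result would correct a misreading.

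**Working it through.** The protocol gives no expected rate, rate ratio or event count for Table 19, so there is no planned figure to reproduce. The check has three parts.

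**1. What the text limits and what it does not.**

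- Section 9.3.5 says users on platelet aggregation inhibitors will be followed, then limits the assessment to consecutive cilostazol use.
- Section 9.3.8 says users will be followed for hospitalisation, and Section 9.7.9 keeps the limit: "with at least one hospitalisation for any cause during consecutive use of cilostazol".
- In Section 9.7.5, Tables 17B and 17C are limited to current users at 3 months and Table 18 to continuous use.
- Section 9.3.6 on visits and Table 19 use the same idea of following patients, with no such limit.

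Read with Section 9.2.6, the natural reading is start date to end of enrolment, death or study end.

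**2. Share of follow-up on treatment.**

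Inputs: period lengths P from Table 2 and Section 9.2.2.1. In years these are THIN 10.58, GePaRD 5.0, Sweden 3.75, SIDIAP 2.91, IACS 2.0 and DUS2 1.0. The documents give no persistence figure, so median time on cilostazol is assumed to be 0.5, 1 or 2 years. Further assumptions are exponential stopping without restarts, uniform entry, and follow-up to the end of the period.

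With L = ln 2 / median:

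- mean on-treatment time = (1/L) × [1 − (1 − exp(−LP)) / (LP)]
- mean follow-up = P/2
- f = mean on-treatment time / mean follow-up

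Example at a 1-year median: THIN 1.25 / 5.29 = 24%; DUS2 0.40 / 0.50 = 80%.

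| | 0.5 y | 1 y | 2 y |
|---|---|---|---|
| THIN, DUS1 | 13% | 24% | 40% |
| GePaRD, DUS1 | 25% | 42% | 61% |
| Sweden, DUS1 | 31% | 50% | 68% |
| SIDIAP, DUS1 | 38% | 57% | 73% |
| IACS, DUS1 | 48% | 66% | 80% |
| DUS2 | 66% | 80% | 89% |

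The share is higher in DUS2 in every column. The gap is large for THIN and small for IACS (9 points at 2 years).

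**3. Effect on the rate ratio.**

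Let c be the background visit ratio (cardiac history versus none), m the multiplier on visits in the cardiac group while on cilostazol, and f the share above. Then

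observed ratio = c × (f × m + 1 − f).

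The documents give neither c nor m, so both are assumed.

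- *No intensified monitoring (m = 1):* the observed ratio equals c at any f. Background ratios of 1.25, 1.5 and 2.0 are reported as 1.25, 1.5 and 2.0. The within-phase ratio is then background only.
- *Same monitoring in both phases (m = 1.5), c unchanged:* c cancels, and the DUS2/DUS1 ratio of rate ratios is (1 + 0.5 × f2) / (1 + 0.5 × f1). At a 1-year median, THIN gives 1.402 / 1.118 = 1.25 and IACS gives 1.402 / 1.331 = 1.05. Over the three persistence values the range is 1.21 to 1.25 for THIN and 1.03 to 1.08 for IACS.

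An apparent increase of this size would arise with no change in monitoring. If m = 1 in both phases, there is no such artefact.

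**The case against.** The strongest reply is that the protocol never says off-treatment visits will be counted. The person-years it defines in Section 9.7.1 (Tables 6 and 7) are person-years of use and of consecutive use, and the table shells are in a separate file not shown here. That stands as a caution: a reader might take on-or-off counting as stated, but it is an inference from Sections 9.2.6 and 9.3.6 and from the missing limit. It is still the natural reading, because the protocol adds the limit elsewhere when it intends one.

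Other stronger readings are also tempting and not supported:

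- *DUS1 is mostly off-treatment time.* Across the assumed range this holds only for THIN. At 2 years' persistence four of the five databases are mostly on treatment. Disenrolment and death also end follow-up, so the model overstates off-treatment time, notably in THIN, where Section 9.4.2 says about one-third of patients are active at any one time.
- *The DUS1 to DUS2 change cannot be interpreted at all.* A stable background ratio cancels in that comparison. What remains is the difference in on-treatment share, which is modest in some databases.
- *The comparison is wholly unadjusted.* The Abstract promises age and sex stratification for all analyses. This does not remove visits caused by the cardiac history itself, and Annex 2 declares confounding not applicable and says that no effect measures are estimated, although Table 19 estimates rate ratios.
- *The confidence intervals are too narrow.* The protocol names no variance method, so there is nothing to criticise on that score.
- *Sweden was overlooked.* Section 9.4.2 discloses that "Visits to GPs and specialists outside the hospitals are not included in the registers" and that hospital outpatient care is recorded at about 80% coverage. What is missing is only a label on the Table 19 result.

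**Conclusion.** The point holds in a limited form. As written, Table 19 does not tie visits or person-time to cilostazol use, although the label measure concerns treatment time and neighbouring analyses carry that limit. Follow-up of up to 2 to 10.6 years in DUS1 against at most 1 year in DUS2 can then shift the rate ratio without any change in monitoring. With a 1.5-fold on-treatment visit rate the shift is about 21 to 25% in THIN and 3 to 8% in IACS. These sizes rest on assumed persistence and an assumed multiplier; the direction rests only on the different period lengths and on some excess of visits on treatment. Separately, the within-phase ratio reflects background visit frequency, even within age and sex strata, and cannot alone show intensified monitoring. This is a cheap improvement to an evaluation that remains usable, not a fault that invalidates the study.

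**What to change.** - In Sections 9.3.6 and 9.7.5 (and the matching line of the Abstract), state that Table 19 visits and person-time are limited to consecutive use of cilostazol, in both DUS1 and DUS2.
- Describe the within-phase ratio of patients with and without cardiac history as descriptive.
- Base any conclusion on the DUS2 versus DUS1 change in on-treatment visit rates, by database.
- Label the Swedish result as hospital outpatient visits only.

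The cost is wording, less person-time in the rates, and rerunning one table in the DUS1 databases that Section 6.1 reports as completed. If the shells already use on-treatment time, one clarifying sentence is enough. The restriction does not equalise time since start: at a 1-year median, mean on-treatment time is about 1.25 years in THIN DUS1 against 0.40 in DUS2, so that difference should be noted when the phases are compared.

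A comparison with each patient's own visit rate in the 6 months before the start date could be an optional sensitivity analysis. It should not replace the main measure, because visits leading up to the prescription can inflate that baseline.

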### **9.7.6 Assessment of Contraindications**

Analysis Table 20: Contraindications for cilostazol currently listed in the SmPC will be assessed at the start date according to the following time frames:

- Diagnosis recorded at any time before the start date: renal failure, liver disease, congestive heart failure, diabetic retinopathy, arrhythmias
- Diagnosis recorded within 6 months before the start date: active peptic ulcer, recent cerebral haemorrhage

The number and percentage of patients with contraindications will be calculated by sex and age group (< 70 years, ≥ 70 years).

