### 9.3.3 Characterisation of New Users at the Start Date

New users of cilostazol will be characterised at the start date according to demographic, family history, comorbidity, and comedications. Comorbidity will be ascertained through primary care and/or hospital discharge diagnosis codes recorded in the study databases at any time before the start date. Comedications will be ascertained through medication codes recorded in the 6 months before the start date.

Some variables may not be available in all databases. For example, smoking status is available only in THIN, and the recording of data may be incomplete.

The following variables will be assessed:

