### **Assessment of Contraindications**

Use of cilostazol will be additionally evaluated for the use in patients with diseases and conditions listed as contraindications in the SmPC. These contraindications are the following:

- Severe renal impairment
- Moderate to severe hepatic impairment
- Congestive heart failure
- History of bleeding disorders: active peptic ulcer, recent haemorrhagic stroke, proliferative diabetic retinopathy, poorly controlled hypertension
- History of arrhythmias: ventricular tachycardia, ventricular fibrillation or multifocal ventricular ectopics, prolongation of the QT interval

The diagnosis codes that will be used to define the variables for the evaluation of contraindications are included in Table 4.

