### **Overall Assessment of Contraindications**

Overall assessment will be conducted by evaluating the number of users who are current smokers at the start date, have a labelled contraindication for the use of cilostazol, or have a new 2013 SmPC contraindication.

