### **9.7.7 Overall Assessment of Contraindications**

Analysis Table 28. Number and percentage of users with new 2013 SmPC contraindications and contraindications labelled before 2013.

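### Analysis Table 20 words four contraindications more broadly than the protocol's own list and leaves a fifth uncounted; separately, the two descriptions of the overall count disagree on smokers

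*Protocol*

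**What the plan says.** Section 9.3.6 (Assessment of Contraindications) sets out which SmPC contraindications will be evaluated. The renal item is "Severe renal impairment", the hepatic item is "Moderate to severe hepatic impairment", and the arrhythmia item reads "History of arrhythmias: ventricular tachycardia, ventricular fibrillation or multifocal ventricular ectopics, prolongation of the QT interval". Under bleeding disorders it names active peptic ulcer, recent haemorrhagic stroke, proliferative diabetic retinopathy and poorly controlled hypertension. Congestive heart failure is also listed. On coding it states: "The diagnosis codes that will be used to define the variables for the evaluation of contraindications are included in Table 4".

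Section 9.7.6, which defines Analysis Table 20, gives one group with unlimited look-back, "Diagnosis recorded at any time before the start date: renal failure, liver disease, congestive heart failure, diabetic retinopathy, arrhythmias", and a second group with a 6-month look-back: active peptic ulcer and recent cerebral haemorrhage.

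The overall assessment is described twice. Section 9.3.6 defines it through the "number of users who are current smokers at the start date, have a labelled contraindication for the use of cilostazol", or who have a new 2013 contraindication. Section 9.7.7 describes Analysis Table 28 as "Number and percentage of users with new 2013 SmPC contraindications and contraindications labelled before 2013".

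**The concern.** Table 20 is presented as the count of SmPC contraindications among new users, and Table 28 as the overall figure. Section 8 says DUS2 is there to evaluate the impact of the SmPC changes and communications on prescribing. If a row includes patients whose condition is not on the protocol's list, its percentage is not the share with that contraindication, and a real change among listed patients is harder to see.

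The protocol also uses a history of arrhythmias elsewhere in a different role. In Table 7, a history of tachyarrhythmias falls under warnings and calls for close monitoring. Analysis Table 19 takes visit rates in patients with a history of arrhythmias as a proxy for that monitoring. With an unrestricted arrhythmia row, the same patient could appear in Table 19 as someone to be monitored and in Table 20 as contraindicated.

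**Working it through.** **1. Listed condition, Table 20 wording and Table 4 code, side by side.**

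| Listed in 9.3.6 | Wording in 9.7.6 | Table 4 |
|---|---|---|
| Ventricular tachycardia, ventricular fibrillation or multifocal ventricular ectopics; QT prolongation | arrhythmias | Arrhythmias row is I47, I48, I49, which includes atrial fibrillation and flutter (I48) and supraventricular tachycardia (I47.1). Separate rows exist for ventricular tachycardia (I47.0, I47.2) and ventricular fibrillation and flutter (I49.0). No separate row for ectopics or QT. |
| Severe renal impairment | renal failure | N17-N19, no severity split |
| Moderate to severe hepatic impairment | liver disease | K70-K77, no severity split |
| Proliferative diabetic retinopathy | diabetic retinopathy | No row; only diabetes mellitus, E10-E14 |
| Poorly controlled hypertension | not counted | I10-I15, with no level of control |

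Four rows are broader than the list and one listed condition is missing. For renal and hepatic disease Table 4 offers nothing narrower. For arrhythmias it offers two ventricular rows that 9.7.6 does not name.

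**2. Direction for a single row.** Within the same data, a broad code set contains every case of the listed condition that it captures, plus others. Its count cannot be lower than that of the captured listed cases.

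**3. Direction for the combined total.** The protocol gives no figure for contraindicated use and no prevalences, so there is nothing to reproduce and the values here are assumptions. Let c be the share with a listed and captured condition, e the share added only by broad codes, and h the share with poorly controlled hypertension, treated as independent.

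- Planned total = 1 − (1 − c)(1 − e)
- Total on the 9.3.6 list = 1 − (1 − c)(1 − h)
- Net error = (1 − c)(e − h)

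With h = 0, the error runs from 0.95 × 0.05 = 4.75 points (c = 5%, e = 5%) to 0.98 × 0.20 = 19.6 points (c = 2%, e = 20%). With c = 5% and e = 10%, the planned total is 1 − 0.95 × 0.90 = 14.5%, and:

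- h = 0: +9.5 points
- h = 10%: 0
- h = 20%: −9.5 points

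The sign depends on whether e exceeds h, which the documents do not tell us.

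**4. Comparison with sampling error.** Table 11 can be checked. Exact binomial limits reproduce 49 of its 50 bounds, and the other differs by 0.1 point. At 1,500 users and 5% the interval is 4.0 to 6.2, about 1.1 points each way. A definitional shift of several points would exceed that.

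**5. Dilution of change (illustration).** Assume 1,500 users per phase (Table 11's smallest size), a listed condition that halves from 2% to 1%, and a constant, non-overlapping 10% added by broad codes.

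- Listed row: SE = √(0.02 × 0.98/1500 + 0.01 × 0.99/1500) = 0.0044; z = 0.01/0.0044 ≈ 2.3
- Broad row, 12% to 11%: SE = √(0.12 × 0.88/1500 + 0.11 × 0.89/1500) = 0.0116; z = 0.01/0.0116 ≈ 0.9

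The absolute change is the same 1 point. The relative change shrinks from one half to one twelfth, and the standard error is about 2.6 times larger.

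**6. Smoking.** Table 7 places smoking under the indication, not the contraindications. Its availability is stated in several ways. Section 9.3.3 says "smoking status is available only in THIN, and the recording of data may be incomplete", and the Table 7 footnote agrees. The text of 9.3.6 and section 9.9 say THIN and GePaRD. Table 9 marks lifestyle risk factors as held in SIDIAP and THIN but not GePaRD, though it does not name smoking. If smokers were counted, and 20% to 40% smoked (assumed) alongside an assumed 10% with a contraindication, the total would be 1 − 0.90 × 0.80 = 28% to 1 − 0.90 × 0.60 = 46% where smoking is recorded, against 10% where it is not.

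**The case against.** The best defence is that 9.7.6 mainly assigns look-back windows to a list already defined in 9.3.6, so its short names need not be case definitions. The abstract shortens the same list in a similar way, and Table 4 contains ventricular codes an analyst could choose. This shows that the arrhythmia wording is ambiguous, and no sentence says atrial fibrillation will be counted as a contraindication. It does not help renal or hepatic disease, for which Table 4 has no narrower code. Nor does it help retinopathy, which has no code, or hypertension, which 9.7.6 omits.

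A second defence is that the study is descriptive, the conditions are named separately, and the same definitions serve both phases. Equal definitions help comparability but do not remove the dilution, and section 9.9 does not tell the reader that these rows are broad.

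Several stronger readings are tempting but unsupported:

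- **That overall contraindicated use is overstated.** The upward direction follows only for individual broadened rows. A listed condition goes uncounted, Sweden has no primary care diagnoses, and IACS data are complete only since 2010 (Table 9). All three pull counts down.
- **That the total cannot fall even if prescribers follow the SmPC.** Table 28 includes the new 2013 contraindications, and listed cases sit inside the broad codes, so it can fall.
- **That smokers are counted in these tables.** They are not in Table 20, and the text for Table 28 does not mention them. Only 9.3.6 does, and the table shells are separate files not shown here.
- **That the arrhythmia row is inflated by some known multiple.** No prevalence is given, so any multiple is an assumption.

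**Conclusion.** The concern holds as an inconsistency between the protocol's list of contraindications and the analysis meant to count them. Four rows of Table 20 are worded more broadly than the list, one listed condition is not counted, and Table 4 lacks codes that 9.3.6 says it contains. Followed literally, the broadened rows include patients without a listed contraindication and weaken the DUS1-to-DUS2 comparison. The dilution illustration assumes that the share added by broad codes stays constant between phases.

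The size of the effect, and the net direction for the combined total, cannot be established from the documents. The smoking point is a conflict between 9.3.6 and 9.7.7 to be resolved, not a settled count. It matters because, if smokers were included, the total would vary by database according to whether smoking is recorded. This should be fixed. Which conditions ought to be contraindications is not judged here.

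**What to change.** Reconcile both contraindication subsections of 9.3.6 with 9.7.6, 9.7.7 and Table 4, so that each listed condition has one definition, one code list and one look-back.

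- **Arrhythmias:** define the row from the ventricular codes already in Table 4 (I47.0, I47.2 and I49.0), and add codes for multifocal ventricular ectopics and QT prolongation.
- **Other listed conditions:** add codes for proliferative retinopathy. Either define poorly controlled hypertension or state that it cannot be ascertained.
- **Severity:** use severity codes, or laboratory results where held (9.4.2 gives SIDIAP laboratory data from 2006), for renal and hepatic impairment. Where severity cannot be coded, label the row a broad proxy and keep it outside the main total in Table 28, with a total including the broad rows as a sensitivity row.
- **Smoking:** remove it from the overall contraindication assessment, report it only in Table 17A, and state once which databases hold it.
- **Both phases:** apply identical definitions to DUS1 and DUS2.

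The cost is more than code-list edits. Section 6.1 records DUS1 as complete in THIN, IACS, SIDIAP and Sweden by 30 January 2015, so Tables 20 and 28 must be rerun on the DUS1 data or comparability is lost. Laboratory values may need further extraction. Narrow definitions will miss cases whose severity is uncoded, which is why the broad rows should remain visible.
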